9.12 Analysis of pharmacoeconomic variables

9.12.1 Change from baseline by visit up to Week 108 in WPAI:MS scores

Analyses will be summarized and listed on the FAS. WPAI scores and number of subjects currently employed by visit during the main study are summarized per treatment group. WPAI-MS outcome measures (absenteeism, presenteeism, overall work impairment and activity impairment) will be graphically presented over time using mean \pm SE.

9.12.2 Health care resource utilization

Health care resource utilization will be summarized and listed on the FAS.

Descriptive summary statistics will be displayed for subjects with at least one and frequency of health care resource utilizations as well as length of stay (days) from baseline up to Week 108 for the following categories: all hospitalizations, hospitalizations due to AE, hospitalizations due to relapse, ICU admissions due to MS relapses, emergency room visits due to MS.

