 (1) FSIQ-RMS symptoms scale will be completed for 7 consecutive days. (2) No ██████████ assessment at Baseline. (3) Non-conventional ██████████ (██████████) at selected sites only. (4) Height only at Visit 1 (Screening). (5) Pre-dose and hourly for at least 4 h post-dose and up to 12 h. (6) Pre-dose and 3 h post-dose. (7) In addition, ALT, AST, INR, alkaline phosphatase and total bilirubin at Weeks 6, 8, 10, 14, 16, 18, 20, and, 22; total white blood cell and total lymphocyte counts at Weeks 8, 16, and 20.
 (8) Pharmacokinetic sampling pre-dose at Weeks 12, 60 and 108, and 3 h post-dose on Day 1 and Week 12.

Table 3 Visit and assessment schedule (Part 2)

Periods	Name	TREATMENT PERIOD				FOLLOW-UP		UNSCHEDULED			
	Duration	108 Weeks				30 Days					
Visits	Number	11	12	13	14	15	16	R1, R2, ...	U1, U2, ...	I1, I2, ...	
	Name	W72	W84	W96	EOT	FU1	FU2	Relapse	Unscheduled (1)	Re-initiation	
	Time	Week 72	Week 84	Week 96	Week 108 or at premature discontinuation	Last study drug intake +15 days	Last study drug intake +30 days	Any day between Day 1 and EOS			
	Visit window	± 7 days	± 7 days	± 7 days	± 7 days	-1 day, +7days	+7 days (22)	+7 days	NA	NA	± 1 day
EDSS/FS*		X	X	X	X		X	X	X		
Relapse*		X<----->X				X	X	X	X		
FSIQ-RMS**			X		X			X	X		
SF-36v2**			X		X			X			
Health care resource utilization*		X	X	X	X			X			
WPAI:MS**			X		X						
(Sub-study)						X					
Chest X-ray*					X						
MRI** (2)					X				X		
eC-SSRS**					X						
Physical examination*			X		X			X	X		
Dermatological examination*, Body weight *					X				X		
SBP/DBP*, 12-lead ECG**		X	X	X	X	X	X	X	X	X(3)	X
Pulse rate*								X	X(4)		
Ophthalmological examination / OCT*					X				X		
PFT incl. spirometry (All) and DL _{CO} (sub-study)**					X	X	X		X		
Hematology/Chemistry**(fasted)		X	X	X	X	X	X		X		
Urinalysis			X		X	X			X		
Viral serology, Serum sample vaccination*									X		
Pregnancy test*/**		X	X	X	X	X	X		X		
PK sampling for ponesimod*					X				X(5)		
Teriflunomide plasma concentration									X(4)		
Accelerated elimination procedure					X	X(4)					
Accelerated elimination procedure compliance						X	X(4)				
Study drug dispensing/accountability		X	X	X	X			X	X	X	X
AEs*/SAEs, Concomitant medications*, Body temperature*		X	X	X	X	X	X	X	X	X	X

*Data collected in the eCRF, **Electronically transferred to sponsor, Day 1 = date of randomization visit,

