(1) Unscheduled visits may include all or some of the indicated assessments. (2) Brain MRI to be performed at any time an opportunistic infection in the CNS is suspected.

Non-conventional [redacted] at selected sites only. Note: MRI assessment at EOT does not need to be performed if the EOT visit occurs within < 4 weeks of the MRI assessment at Visit 10. (3) Pre-dose and hourly for at least 4 h post-dose and up to 12 h. (4) If needed (see protocol for details). (5) When possible, collect PK sample upon experiencing SAE.

Table 4 Visit and assessment schedule (Part 3)

Periods	Name	POST-TREATMENT OBSERVATION PERIOD (PTOP) (to be performed after EOT)		
	Duration	Up to 108 Weeks		
Visits	Number	6A, 8A, 9A, 11A,13A	7A, 12A	10A, 14A
	Name	W12A, W36A, W48A, W72A, W96A	W24A, W84A	W60A, W108A
	Time	Week 12-36-48-72-96	Week 24 and 84	Week 60 and 108
	Visit window	±7 days	±7 days	±7 days
EDSS/FS*	X	X		X
Relapse*		X<----->X		
MRI*				X
FSIQ-RMS** (1), [REDACTED]**, [REDACTED]*	X (only Week12)	X		X
Concomitant medications*	X	X		X
Physical examination*				X
Dermatological examination*				X
SBP/DBP*	X	X		X
12-lead ECG **				X
Body temperature*	X	X		X
PFT incl. spirometry (All) and DL _{CO} (sub-study)**				X (Week 108 only)
Hematology/Chemistry** (fasted)		X		X
Urinalysis*		X		X
Pregnancy test*/**	X	X		X
AEs/SAEs *	X	X		X

*Data collected in the eCRF, **Electronically transferred to sponsor, Day 1 = randomization visit. If the first PTOP visit windows overlaps with FU1 or FU2 visits, visits and assessments can be combined.

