- Intensive Care Unit (ICU) admissions for MS Relapses: Derived from the ‘Intensive Care Unit Admissions for MS Relapses’ form and includes all admissions (irrespectively if due to MS relapse or due to MS)
- Emergency room visits for MS relapses: Derived from the ‘Intensive Care Unit Admissions for MS Relapses’ form and includes visits due to MS relapse and due to MS. Note that emergency room visits are not considered hospitalizations.

The length of stay (in days) per admission is defined as: Length of hospitalization = End date of hospitalization – Start date of hospitalization + 1 (in days).

The length of stay (in days) from baseline to Week 108 per category taking into account multiple encounters is derived as the sum of length of stay across all admissions / visits only considering days from baseline (randomization date) to Week 108 (Day 756). In case of overlapping hospitalizations, each day is counted only once.

The number of admissions / visits from baseline to Week 108 is defined as a count variable per category. Two hospitalizations with identical admission date will be counted as one hospitalization.

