7.1.2 Full analysis set

The Full Analysis Set (FAS) includes all randomized subjects.

In order to preserve the randomization, subjects will be evaluated according to the treatment they have been randomized to.

The main analyses of the primary and all secondary endpoints will be based on the FAS. For the efficacy analyses on the FAS, unless otherwise stated, all available efficacy data up to the EOS will be included.

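### Health care resource use is summarised as raw counts to Week 108 with no observation time, so time after study withdrawal counts as no use; ICU and emergency visits also lose scheduled collection at premature end of treatment

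*SAP*

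**What the plan says.** SAP Section 9.12.2: "Health care resource utilization will be summarized and listed on the FAS". Section 7.1.2: "The Full Analysis Set (FAS) includes all randomized subjects". The summaries are descriptive: subjects with at least one use, and the "frequency of health care resource utilizations as well as length of stay (days) from baseline up to Week 108", in five categories (all hospitalizations, those due to adverse events, those due to relapse, ICU admissions, emergency room visits).

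Section 5.7.2 defines the variables: "The number of admissions / visits from baseline to Week 108 is defined as a count variable per category". Length of stay is summed over admissions, "only considering days from baseline (randomization date) to Week 108 (Day 756"). Neither definition has an observation time, a cut at EOS or EOT, or a rule for subjects whose collection ends early.

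The same section names the sources. Adverse-event hospitalizations come from the adverse event form and relapse hospitalizations from the relapse summary form. ICU admissions and emergency visits come from dedicated forms.

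In Section 2.2, the row "Health care resource utilization" in Tables 2 and 3 is marked at treatment-period visits from Week 2 through EOT and at unscheduled relapse visits. Those relapse visits may fall on any day up to EOS. Table 4, headed "POST-TREATMENT OBSERVATION PERIOD (PTOP) (to be performed after EOT"), has rows for relapse and for adverse events, but none for resource use.

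**The concern.** A count over a fixed 108-week window is interpretable only if every subject is observed for the whole window, or if the unobserved time is accounted for. Here a subject with no record after leaving the study is indistinguishable from one who was followed and used nothing. The counts, the proportion with at least one use and the days of stay are all pulled downwards, and more so in the arm with more or earlier loss. For ICU and emergency visits the loss can begin at premature EOT, while the subject is still in the study.

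The SAP treats other counts differently. It defines an observation time for the annualized relapse rate (Section 5.4.1), for the cumulative lesion count (5.4.2.2) and for treatment-emergent adverse events (5.5.2.1). It also reports adverse events of special interest over cumulative subject-years (9.10.2.4.1). At stake is a descriptive comparison between arms whose Week 108 label is not true of every subject in the table.

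**Working it through.** The SAP gives no figure for this analysis to reproduce, apart from the window: 108 × 7 = 756 days, which agrees with Section 5.7.2.

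**Coverage by category** (Section 5.7.2 sources against Section 2.2 schedules):

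| Category | Source form | Collected in the post-treatment observation period? | After study withdrawal? |
|---|---|---|---|
| Hospitalization, adverse event | Adverse event | Yes (Table 4) | No |
| Hospitalization, relapse | Relapse summary | Yes (Table 4) | No |
| Any hospitalization | The two above plus ICU form | Mostly | No |
| ICU admission | ICU form | Only at relapse visits (Table 3) | No |
| Emergency visit | Dedicated form | Only at relapse visits (Table 3) | No |

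Section 5.7.2 first takes emergency visits from the emergency facility form and later derives them from the ICU form. That needs reconciling, but either form gives the same coverage.

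**Size of the gap.** All inputs below are assumptions, because the SAP gives no rates. Let *d* be the share stopping treatment early, *f* the mean stopping time as a fraction of 108 weeks, and *u* the share of later ICU or emergency use that is not captured. With a constant true rate, the share of expected use lost is

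loss = *d* × (1 − *f*) × *u*

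- *d* = 10%, *f* = 0.50, *u* = 0.5: 0.10 × 0.50 × 0.5 = 2.5%
- *d* = 10%, *f* = 0.50, *u* = 1: 5%
- *d* = 20%, *f* = 0.50, *u* = 1: 10%
- *d* = 30%, *f* = 0.25, *u* = 1: 0.30 × 0.75 × 1 = 22.5%

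For study withdrawal, which affects all five categories, the same formula applies with the withdrawal share in place of *d* and *u* = 1. For example, 10% withdrawing evenly over time gives 5%.

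**Between arms**, equal true rates, *f* = 0.50, *u* = 1:

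- 15% against 15%: 0.925 / 0.925 = 1.00
- 15% against 20%: 0.925 / 0.90 = 1.03
- 10% against 20%: 0.95 / 0.90 = 1.06. Inverted, 0.90 / 0.95 = 0.947, about 5% lower in the arm with more stopping.

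If relapse visits capture half of the later use (*u* = 0.5), the last contrast becomes (1 − 0.05) / (1 − 0.025) = 0.95 / 0.975 = 0.974, about 2.6% lower.

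**The case against.** The strongest reply is that most of the data are still collected. Adverse-event and relapse hospitalizations run through the post-treatment observation period. Even ICU and emergency use is recorded at relapse visits up to EOS, and visits made for MS are the ones most likely to lead to a relapse visit. This stands. A reader of Table 4 alone might infer that resource-use collection as a whole ends at premature EOT, or that someone who stops at Week 20 and later attends an emergency room is always recorded as having no visit. The source forms and Table 3 do not support either inference.

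A second reply is that nothing here is tested, so an offset of the kind used for relapse rate or lesions is not needed. It is true that no model is required. However, the SAP also gives observation time to its descriptive adverse event counts, so a denominator would not be unusual.

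Third, Section 9.3.1 already displays time in study and time on treatment by arm, with cumulative totals. This helps a reader to see differential follow-up. But those totals sit in another table and are not capped at Day 756, and for subjects who complete treatment, time in study runs into the safety follow-up after Week 108.

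Two caveats remain. The SAP never says that uncollected time is zero; this follows from the plain count definition. Table 4 also has redacted cells. Since the row is visible in Tables 2 and 3, a hidden one is unlikely, though not excluded.

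**Conclusion.** The point holds in two parts. For every category, the absence of an observation time means that follow-up lost to study withdrawal before Week 108 counts as no use. For ICU admissions and emergency visits only, use during the post-treatment observation period that is not captured at a relapse visit is lost as well.

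The size cannot be determined from the SAP. The difference of about 5% between arms rests on assumed early stopping of 10% and 20%, even timing, a constant rate and no capture after EOT. A reader might take it as an estimate of bias. It is not one: any capture at relapse visits shrinks it, and for that assumed contrast it is the upper end. Nor does the plan support saying that one arm would look cheaper, since it analyses counts and days and not costs.

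The impact is minor. The summaries are descriptive, sit outside the multiple testing strategy of Section 9.1.1, and bear on no efficacy claim.

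**What to change.** In Section 5.7.2, define observation time for each subject as randomization to min(EOS, Day 756). In Section 9.12.2, add by arm the total events and days, the cumulative subject-years and the rates per subject-year, next to the planned counts.

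For ICU admissions and emergency visits, keep all captured events to EOS in the main summary. Footnote that scheduled collection ended at premature EOT. Add a supportive rate restricted to randomization to min(EOT, Day 756), with a stated rule for randomized subjects who were never treated and so have no EOT. Cutting the main summary at EOT is not recommended: it would discard real events recorded at relapse visits and depart from the up-to-EOS approach to pharmacoeconomic data in Section 11.4.

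The same edit can settle which form supplies the emergency visits.

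The cost is one derived variable (plus its EOT-restricted counterpart) and a few table rows. No new data are needed. The proportion with at least one use is not corrected by a rate, so it should be read beside the subject-years.

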9.13 Analysis of pharmacodynamic variables

Descriptive analyses of lymphocyte data are described in Section 9.10.5. Only lymphocyte counts from central laboratory, irrespective of whether obtained at a scheduled or unscheduled visit, are included in any of the below describe analyses.

For each subject in the SAF, the

- Nadir (i.e., lowest) treatment-emergent lymphocyte value (up to EOT + 15 days)

is identified and summarized by means of frequency counts and percentages based on the categories specified in Section 5.8.

Lymphocyte counts and percent change from baseline in lymphocyte counts at the following time points [for definition, see Section 5.8] are summarized using descriptive

statistics and displayed graphically by box-and-whisker plots visualizing mean, median, interquartile ranges, SD, and outliers over time: Baseline, Last on-treatment, Day-15 follow-up (plus one display adding Day-30 follow-up in addition). Only subjects with data available at all three (four) time points are included. Corresponding descriptive data is tabulated.

Individual absolute and percent change from baseline in lymphocyte counts to last assessment on treatment versus absolute and percent change from baseline to last follow-up is graphically presented by means of scatterplots with treatment groups color-coded.

9.14 Analysis of pharmacokinetic variables

Will be detailed in a separate analysis plan.

10 GENERAL STATISTICAL METHODOLOGY

This section describes in general terms the statistical models and methods applied.

10.1 Statistical methodology for count data

Count data will be analyzed assuming data is negative binomially (NB) distributed.

A generalized linear model with NB distribution will be assumed.

t_j denotes the length of observation for subject j .
 Y_j denotes the counts of interest for subject j during t_j .
 μ_j denotes the mean of the NB distribution of Y_j .

The mean for the distribution of the ARR for subject j , denoted by μ_j/t_j , will be modeled by the following equation:

$$\log(\mu_j/t_j) = \mathbf{x}'_j \boldsymbol{\theta}, \text{ i.e., } \log(\mu_j) = \mathbf{x}'_j \boldsymbol{\theta} + \log(t_j), \text{ where}$$

\mathbf{x}_j is the vector denoting study treatments and covariates for subject j
 $\boldsymbol{\theta}$ is the vector of unknown fixed-model parameters.

The SAS code for the NB model with 99% CI is as follows (considered “draft” until fully validated at analysis stage):

```
proc genmod data=ADREL;
  class Treat Strat Covar;
  model COUNTS = Treat Strat Covar / dist=negbin link=log
  offset = offset;
  lsmeans Treat / cl exp alpha = 0.01 OM;
  estimate 'Ponesimod - Teriflunomide' || Treat 1 -1 / exp alpha = 0.01;
run;
```

The offset variable used will be specified per analysis (e.g. for ARR it is the log-transformed observation time, for total T1 lesions it is the log-transformed number of available MRI scans, ...).

The 'LSMEANS' statement will output the mean estimates for each of the treatment arms with 99% Wald CIs; the option OM ensures that the mean is derived for categorical covariates with weights as per observed marginal proportions.

The 'ESTIMATE' statement will output the rate ratio of the treatment effect with 99% Wald CIs. The direction of the estimate statement (governed by '1 - 1' or '-1 1') is chosen such that the rate ratio relative to teriflunomide is provided (with rate ratio < 1 indicating ponesimod is better).

To obtain 95% CIs the option alpha = 0.05 is used in the LSMEANS and ESTIMATE statements.

The number of covariates / stratification variables included in the model is different from analysis to analysis, and these are described in the respective analysis sections [see Section 9]. Interaction terms might be included in the model, depending on the analysis.

If the NB distribution is not considered to be appropriate (e.g. due to non-convergence), other distributions such as the Poisson and zero-inflated Poisson will be explored. For the Poisson distribution, a Poisson regression is conducted with model equation identical to the one for the negative binomial regression. The SAS code is as follows (considered "draft" until fully validated at analysis stage):

```
proc genmod data=ADREL;
  class Treat Strat Covar;
  model COUNTS = Treat Strat Covar / dist=poisson link=log
  offset = offset;
  lsmeans Treat / cl exp alpha = 0.01;
  estimate 'Ponesimod - Teriflunomide' || Treat 1 -1 / exp alpha = 0.01;
run;
```

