5.4 Efficacy variables

5.4.1 Primary efficacy variable(s): ARR up to EOS

The primary endpoint is the Annualized Relapse Rate (ARR) up to EOS, based on confirmed relapses according to the treating neurologist / principal investigator. ARR is defined as the number of confirmed relapses per subject-year.

For subjects completing the study as planned the EOS is scheduled to occur at least 108 weeks (± 7 days) after randomization.

More precisely, for subjects prematurely discontinuing treatment the EOS is scheduled to occur 108 weeks (± 7 days) after randomization. For subjects completing the 108-week treatment period the EOS is scheduled to occur prior to entry into the open-label extension (14–22 days after EOT, or 23–37 days after EOT in exceptional cases) or after the safety follow-up period for subjects not entering the open-label extension (30–37 days after EOT).

A confirmed relapse is defined as a record with ‘Relapse meeting the criteria for a confirmed relapse?’ answered ‘Yes’ on the ‘Relapse Summary’ eCRF. All confirmed relapses from randomization up to EOS will be included in the analysis.

For the statistical analysis of ARR, the following data will be used:

- Number of confirmed relapses from date of randomization up to EOS date;
- Length of observation expressed in years, defined as: $[\text{EOS date} - \text{date of randomization} + 1]$ in days, divided by 365.25.

The logarithm of the length of observation up to EOS will be used as an offset variable in the primary efficacy and sensitivity analyses.

Confirmed relapses ‘from date of randomization up to EOS date’ includes all confirmed relapses unless starting prior to randomization.

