9.6.3 Main analysis

The primary statistical analysis will be performed up to EOS on the FAS using an NB regression model for confirmed relapses, with treatment as a factor and the binary stratification variables (EDSS \leq 3.5 versus EDSS $>$ 3.5; DMT within last 2 years prior to randomization [Yes/No]) and the number of relapses in the year prior to study entry (categories \leq 1 [or missing, in order to avoid excluding subjects from the analysis] and \geq 2) included in the model. The model also includes an offset variable defined as the log of time on study (in years) from randomization up to EOS. The primary null hypothesis will be tested with a two-sided alpha level of 1% for conclusive evidence and 5% for a positive study.

Mean model-based estimates of the ARR (for confirmed relapses), by treatment arm, as well as 99% CIs and 95% CIs are presented. A rate ratio comparing ponesimod 20 mg with teriflunomide 14 mg will be derived from the model including 99% CIs, 95% CIs and the corresponding p-value. The dispersion parameter will also be displayed.

Descriptive summary statistics of the number of confirmed relapses as a continuous variable and the number of confirmed relapses in categories (0, 1, 2, 3, 4, ≥ 5), by treatment arm will be presented. The total cumulative number of confirmed relapses, as well as the total cumulative time on study (summed for all subjects) will also be displayed. From the total number of confirmed relapses and the total time on study the raw unadjusted ARR, by treatment arm, will be calculated and summarized.

The fit of the model will be assessed and other distributions such as the Poisson distribution will be considered in case of a lack of fit. The treatment-by-covariate interactions will also be assessed in separate models; if the interaction p-value is < 0.01 it will be investigated further to determine the nature of the interaction (quantitative or qualitative).

Handling of study discontinuation

For the main analysis it is assumed that follow-up time after study discontinuation is missing at random: a hypothetical scenario is considered assuming that subjects who discontinued the study would have similar efficacy as the subjects from the same treatment group who did not discontinue the study.

Sensitivity analyses on this assumption are described in Section [9.6.4](#).

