9.7.2.2 Statistical analysis

The main analysis of the secondary endpoint CUAL will be performed on the FAS using a negative binomial regression model with treatment as a factor and the binary stratification variables (EDSS \leq 3.5 versus EDSS > 3.5; DMT within last 2 years prior to randomization [Yes/No]) and Gd+ T1 lesions at baseline (absent or present) included in

the model. The model also includes an offset variable defined as the log of the time up to last MRI (in years) considered for analysis.

Mean model-based estimates of the number of CUALs per year will be provided by treatment group, as well as 95% Wald CIs. A rate ratio comparing ponesimod 20 mg with teriflunomide 14 mg will be derived from the model including 95% Wald CIs and the corresponding p-value. The dispersion parameter will also be displayed.

The fit of the model will be assessed and other distributions such as the Poisson distribution will be considered in case of a lack of fit.

Descriptive summary statistics of the number of CUALs up to Week 108 continuous and in categories (0, 1–5, 6–10, 11+) will be presented. The total number of CUALs as well as the total cumulative time up to the last MRI scan (summed for all subjects) will also be displayed. From the total number of CUALs and the total cumulative time up to the last MRI scan the raw number of CUALs per year will be calculated and summarized.

A listing of CUAL data will be presented.

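### The arm-level mean ARR and CUALs per year are back-transformed log-scale LS-means, so they are rates at the average covariate profile and fall below the mean rate whenever a covariate has an effect

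*SAP*

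**What the plan says.** Section 10.1 of the SAP specifies the count model with "model COUNTS = Treat Strat Covar / dist=negbin link=log" and obtains the arm estimates from "lsmeans Treat / cl exp alpha = 0.01 OM". The accompanying text states: "The 'LSMEANS' statement will output the mean estimates for each of the treatment arms with 99% Wald CIs". It adds that "the option OM ensures that the mean is derived for categorical covariates with weights as per observed marginal proportions".

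These outputs feed two results sections. Section 9.6.3 (primary endpoint): "Mean model-based estimates of the ARR (for confirmed relapses), by treatment arm, as well as 99% CIs and 95% CIs are presented". Section 9.7.2.2 (CUAL): "Mean model-based estimates of the number of CUALs per year will be provided by treatment group". Section 5.4.1 gives the meaning of the primary variable: "ARR is defined as the number of confirmed relapses per subject-year".

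Both models adjust for the EDSS and prior-DMT strata. The ARR model adds prior-year relapses (≤ 1 or ≥ 2); the CUAL model adds baseline Gd+ T1 lesions (absent or present).

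Other relevant provisions:
- Sections 9.6.3 and 9.7.2.2 also call for raw rates (total events over total time).
- Section 9.6.4.1 refits the ARR model with treatment alone, to show what covariate adjustment does. Section 9.6.5.8 prints the arm ARRs from the adjusted and unadjusted models in one forest plot.
- Section 9.6.1 makes the rate ratio the summary measure of the primary estimand.
- The document history in Appendix E records that version 2.0 moved the arm estimates to observed margins.
- The Poisson fallback code in Section 10.1 has no OM option.

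**The concern.** A reader of the study report will take a model-based mean ARR as relapses per subject-year in that arm, averaged over patients like those in the trial. With a log link, that is not what an exponentiated LS-mean is. OM removes the artificial equal weighting of covariate levels but does not change the scale on which the averaging is done.

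Two things are at stake. First, the adjusted arm-level rates for the primary endpoint and for a secondary endpoint would be systematically low, by an amount that depends on how strongly the covariates predict. Second, unlike quantities would be compared. The raw rates and the treatment-only ARR model estimate mean rates; the adjusted model's arm rates do not. The gap in arm ARRs in the Section 9.6.5.8 forest plot would partly reflect the back-transformation, yet Section 9.6.4.1 invites the reader to attribute it to covariate adjustment.

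**Working it through.** **Plan's own figure.** The SAP states no arm rate, covariate prevalence or covariate effect on this point, so there is nothing to reproduce. The prevalences and effects below are assumptions; only the model form and the 1133 subjects come from the SAP.

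**Algebra.** Write the fitted log annual rate as a + b·t + x′g, with t the treatment indicator and x the covariates.
- LSMEANS with EXP and OM: exp(a + b·t + Σ pₖgₖ), where pₖ is the observed proportion at level k. This is a weighted geometric mean of the covariate-specific rates.
- Mean rate over subjects: (1/N) Σᵢ exp(a + b·t + xᵢ′g).

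The exponential is convex, so the first is never above the second. They are equal only if x′g is the same for every subject. The term exp(a + b·t) cancels from their ratio, so both arms shrink by the same factor and the rate ratio is exp(b) either way.

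**Size for one binary covariate** with prevalence p and rate ratio R:

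LS-mean / mean = R^p / (1 − p + pR)

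At p = 0.4:

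| R | R^0.4 | 0.6 + 0.4R | Ratio |
|---|---|---|---|
| 2 | 1.320 | 1.4 | 0.943 |
| 3 | 1.552 | 1.8 | 0.862 |
| 4 | 1.741 | 2.2 | 0.791 |

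At R = 1.2 and 1.5 the ratio is 0.996 and 0.980. For independent covariates the ratios multiply.

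**ARR**, assumed prevalences 0.2, 0.4 and 0.4 with a common R:

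| R | Ratio |
|---|---|
| 1.2 | 0.989 |
| 1.3 | 0.978 |
| 1.5 | 0.947 |
| 1.75 | 0.900 |
| 2.0 | 0.850 |

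That is about 1% to 15% low.

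**CUAL**, assumed strata effects R = 1.2 and Gd+ prevalence 0.3 to 0.5:

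| Gd+ R | Ratio |
|---|---|
| 1.5 | 0.973–0.975 |
| 2 | 0.936–0.941 |
| 3 | 0.856–0.863 |
| 4 | 0.786–0.795 |

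That is about 3% to 21% low.

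The ranges overlap: ARR covariates at R = 1.75 (0.900) give a larger shortfall than Gd+ at R = 2 (0.936 or higher).

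**Simulation check.** 200 negative binomial regressions per scenario, n = 1133, 1:1 allocation, log-time offset, dispersion held at its simulated value. Average arm rates, teriflunomide then ponesimod:

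| Scenario (assumed) | LS-mean | Averaged prediction | Raw | Rate ratio, either way |
|---|---|---|---|---|
| ARR: prevalences 0.2/0.4/0.4, R 1.3/1.3/1.5 | 0.342, 0.242 | 0.355, 0.251 | 0.355, 0.250 | 0.71 |
| CUAL: Gd+ 0.4, R = 3; strata R = 1.1 | 2.49, 1.22 | 2.90, 1.42 | 2.90, 1.42 | 0.49 |
| CUAL: Gd+ 0.4, R = 2; strata R = 1.1 | 2.09, 1.04 | 2.23, 1.11 | 2.23, 1.11 | 0.50 |

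The LS-means are about 3.6%, 14% and 6% low. The averaged predictions track the raw rates. With all covariate effects set to 1, the two methods agree apart from estimation noise (1.500 against 1.504; 0.751 against 0.753).

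**The case against.** The best case for leaving the plan alone has four parts.

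**Nothing confirmatory moves.** The primary summary measure is the rate ratio, Sections 9.6.2 and 9.7.2.1 speak of relative reductions, and the ratio is identical under both methods. This stands in full. A reader might infer that treatment effects on the absolute scale are being misreported, but the SAP plans no absolute rate difference for ARR or CUAL. The exposure is limited to arm rates quoted, or later subtracted, by others.

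**Mean rates are already available.** Raw rates are tabulated for both endpoints. For ARR, the treatment-only model supplies a marginal arm rate with 99% and 95% CIs. For CUAL, the subgroup analyses follow the primary-endpoint method and include baseline Gd+ status, so treatment-only rates by Gd+ level will be shown. This mitigates, but it does not make the adjusted figures mean rates, and no unadjusted overall CUAL model is specified.

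**The plan is open about its method.** The link, EXP and OM are all visible, the code is marked as draft, and the OM sentence describes the weights correctly. Nor does the estimand name an arm-level mean as its target, so it would go too far to say that the estimates miss a defined estimand. But the text as well as the code calls the output a mean, and nowhere says that the averaging is on the log scale.

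**The CUAL emphasis depends on inputs.** It is tempting to say that CUAL is hit hardest, because its extra covariate is baseline MRI activity. That is plausible, but the SAP gives no prevalence or effect to establish it, and the ranges above overlap.

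**Conclusion.** The point holds as one about the reported arm-level rates. As specified, they are rates at the average covariate profile, at or below the covariate-averaged mean rate, and strictly below it whenever a covariate has an effect. The direction is certain; the size is not. Under the assumed prevalences and effects it is about 1–15% for ARR and 3–21% for CUAL, and it vanishes if no covariate predicts. The percentages assume independent binary covariates and the planned model without treatment-by-covariate interaction.

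The rate ratio, its CI and its test are untouched. The practical harm is adjusted arm rates that read low, and a difference between adjusted and unadjusted arm ARRs that could be mistaken for an effect of covariate adjustment.

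**What to change.** In Sections 9.6.3, 9.7.2.2 and 10.1, define each arm's adjusted rate by standardization. From the fitted model, predict every analysed subject's annual rate under ponesimod and under teriflunomide, then average over subjects. Give delta-method or bootstrap 95% CIs for both endpoints, and 99% CIs for ARR as well. Keep the rate ratio from the ESTIMATE statement.

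If the LSMEANS values are retained, label them in text, tables and forest plots as rates at the average covariate profile, and note that they are not directly comparable with the raw or unadjusted rates.

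Apply the same choice to the Poisson fallback. Without OM, its arm estimates would weight covariate levels equally and so differ from the main analysis for a further reason.

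The cost is a short post-estimation step and a few sentences in the SAP. If any covariate predicts, the reported rates will be somewhat higher in both arms, by the same proportion.
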